**Comparison of outcome measures before and after treatment:**

**Table 11: Comparison between outcome measures before and after treatment in group A (Dienogest):**

	Mean	SD	t*	P value
VAS score for dysmenorrhea before	7.10	2.88	7.74	0.00
VAS score for dysmenorrhea after	1.35	2.35		
Hemoglobin level before	10.54	1.65	2.78	0.01
Hemoglobin level after	10.99	1.41		
	Median	IQR	Z**	P value
Leiomyoma volume (cm3) before	15.53	4.31-25.01	2.78	0.01
Leiomyoma volume (cm3) after	19.54	8.25-32.61		
HMB assessment (PBAC) before	70.00	15.00-110.00	2.88	0.004
HMB assessment (PBAC) after	0.00	0.00-8.50		

\*Paired-samples t test    \*\* Wilcoxon Signed Ranks Test

Significant improvements are observed in VAS scores, HMB assessment, and hemoglobin levels after treatment, suggesting that Dienogest is effective. But leiomyoma volume is significantly increased after treatment.

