### **Sample Size:**

The study will be conducted on 40 women; they will be subdivided into 2 equal groups.

Group (A): women will receive Dienogest, with brand name GYNOPROGEST, 2mg pills daily for 3 months (20 cases) (*Ichigo et al., 2011*)

Group (B): women will receive NAC, with brand name GEMACYSTINE, orally at a dose of 600 mg/day for 3 months ( 20 cases) (*Aghaamoo et al., 2021*)

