**Table 7: Comparison between two groups regarding volume of leiomyoma before and after treatment (largest lesion):**

[figure not shown]
	Group A (Dienogest) (N=20)			Group B (NAC) (N=20)			Z*	P value
	Range	Median	IQR	Range	Median	IQR		
Leiomyoma volume (cm  ) before	1.43-45.24	15.53	4.31-25.01	1.00-108.00	9.00	4.09-14.32	0.52	0.61

Leiomyoma volume (cm  ) after	2.66-76.36	19.54	8.25-32.61	3.24-115.90	13.13	7.74-24.16	0.50	0.63
---	------------	-------	------------	-------------	-------	------------	------	------

\*Mann Whitney U test

Median leiomyoma volume slightly increases after treatment in both groups, but the differences between the groups are not statistically significant ( $p > 0.05$ ), indicating that both treatments had similar effects on leiomyoma volume.

[figure not shown]

[figure not shown]

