**Table 8: Comparison between two groups regarding dysmenorrhea VAS score before and after treatment:**

	Group A (Dienogest) (N=20)			Group B (NAC) (N=20)			t*	P value
	Range	Mean	SD	Range	Mean	SD		
VAS score for dysmenorrhea before	2.00-10.00	7.10	2.88	5.00-10.00	7.30	1.78	0.26	0.79
VAS score for dysmenorrhea after	.00-8.00	1.35	2.35	1.00-7.00	3.70	1.69	3.64	0.001

\*Student t test

A significant reduction in VAS scores for dysmenorrhea is observed in both groups after treatment, with Group A showing a more pronounced improvement ( $p = 0.001$ ).

[figure not shown]

[figure not shown]

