**Table 9: Comparison between two groups regarding HMB assessment before and after treatment:**

	Group A (Dienogest) (N=20)			Group B (NAC) (N=20)			Z*	P value
	Range	Median	IQR	Range	Median	IQR		
HMB assessment (PBAC) before	10.00-200.00	70.00	15.00-110.00	10.00-200.00	50.00	15.00-90.00	0.9	0.86
HMB assessment (PBAC) after	.00-200.00	.00	.00-9.00	3.00-200.00	25.00	15.00-70.00	4.10	0.00

\*Mann Whitney U test

Group A shows a significant reduction in PBAC scores after treatment, indicating a better response to treatment compared to Group B (P value = 0.00).

[figure not shown]

[figure not shown]

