**Table 10: Comparison between two groups regarding hemoglobin level before and after treatment:**

	Group A (Dienogest) (N=20)			Group B (NAC) (N=20)			t*	P value
	Range	Mean	SD	Range	Mean	SD		
Hemoglobin level before	7.60-12.80	10.54	1.65	9.30-13.60	11.39	1.46	1.73	0.09
Hemoglobin level after	8.20-13.20	10.99	1.41	7.90-13.80	11.63	1.51	1.39	0.17

\*Student t test

While hemoglobin levels increase slightly in both groups after treatment, the differences between the groups are not statistically significant ( $p > 0.05$ ).

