**Table 12: Comparison between outcome measures before and after treatment in group B (NAC):**

	Mean	SD	t*	P value
VAS score for dysmenorrhea before	7.30	1.78	6.49	0.00
VAS score for dysmenorrhea after	3.70	1.69		
Hemoglobin level before	11.39	1.46	1.40	0.18
Hemoglobin level after	11.63	1.51		
	Median	IQR	Z**	P value
Leiomyoma volume (cm3) before	9.00	4.09-14.32	3.46	0.001
Leiomyoma volume (cm3) after	13.13	7.74-24.16		
HMB assessment (PBAC) before	50.00	15.00-90.00	1.78	0.08
HMB assessment (PBAC) after	25.00	15.00-70.00		

\*Paired-samples t test    \*\* Wilcoxon Signed Ranks Test

Similar to Group A, Group B also shows significant improvements in VAS scores and increase in leiomyoma volume, though the changes in hemoglobin levels and HMB assessments are less pronounced.

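### The efficacy statement for dienogest under SAP Table 11 rests on before-after tests within one of two active arms; it should rest on the randomised comparison with NAC

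*SAP*

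**What the plan says.** The protocol (Sample Size) enrolls 40 women and says "they will be subdivided into 2 equal groups": dienogest in group A and NAC in group B. Study procedures and interventions describes the same two arms, and no placebo or untreated group appears anywhere. The introduction closes with a comparative aim, NAC against dienogest on leiomyoma volume, and Outcomes makes volume primary.

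SAP Table 11 gives paired t and Wilcoxon tests for dienogest alone. The comment below it reads: "Significant improvements are observed in VAS scores, HMB assessment, and hemoglobin levels after treatment, suggesting that Dienogest is effective". The next sentence adds: "But leiomyoma volume is significantly increased after treatment". Table 12 does the same for NAC and comments: "Similar to Group A, Group B also shows significant improvements in VAS scores and increase in leiomyoma volume".

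The between-arm results are in Tables 7 to 10:
- Volume (Table 7): "Median leiomyoma volume slightly increases after treatment in both groups, but the differences between the groups are not statistically significant".
- VAS (Table 8): improvement in both groups, "with Group A showing a more pronounced improvement".
- PBAC (Table 9): a post-treatment advantage for dienogest, Z = 4.10.
- Hemoglobin (Table 10): "While hemoglobin levels increase slightly in both groups after treatment, the differences between the groups are not statistically significant".

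**The concern.** Randomisation protects the contrast between the arms. It does not protect a change over time within one arm, which combines any drug effect with placebo response, regression to the mean and the natural course of symptoms. Without an untreated group the trial cannot divide the change among these. The Table 11 comment nevertheless moves from within-arm significance to effectiveness and cites no between-arm result.

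The SAP's own tables show where that reasoning leads. It would also make NAC effective for pain, because VAS fell significantly there (paired t = 6.49). It would make both drugs enlarge fibroids, because volume rose significantly in each arm (P = 0.01 and P = 0.001). Hemoglobin is the plainest case: it is listed as evidence of efficacy, yet the randomised comparison shows no significant difference.

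At stake is what the trial is taken to have concluded: a standalone efficacy finding for dienogest on three secondary measures, or a comparison with NAC that holds on some outcomes and is not shown on others.

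**Working it through.** **Inputs.** n = 20 per arm. VAS and hemoglobin means and SDs are from Tables 8 and 10, paired t values and within-arm Z values from Tables 11 and 12, and between-arm Z values from Tables 7 and 9. The SAP states no unit for hemoglobin.

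**1. The SAP's own tests reproduce.** With 19 df, the dienogest VAS t = 7.74 gives P < 0.000001 and hemoglobin t = 2.78 gives P = 0.012. Volume Z = 2.78 gives P = 0.005, and PBAC Z = 2.88 gives P = 0.004. These agree with Table 11 to rounding. Between arms, post-treatment VAS has SE = sqrt((2.35² + 1.69²)/20) = 0.647 and t = 2.35/0.647 = 3.63, P = 0.0008 (stated 3.64, 0.001). Post-treatment hemoglobin gives t = 1.39, P = 0.17, as stated. The tests are sound; the issue is which of them carries the conclusion.

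**2. Within-arm changes.** SD of change = |mean change| / paired t × sqrt(20).

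| | Dienogest | NAC |
|---|---|---|
| VAS change | 1.35 - 7.10 = -5.75 | 3.70 - 7.30 = -3.60 |
| SD of change | 5.75/7.74 × 4.472 = 3.32 | 3.60/6.49 × 4.472 = 2.48 |
| 95% CI, t(19) | -7.30 to -4.20 | -4.76 to -2.44 |
| Hemoglobin change | 10.99 - 10.54 = +0.45 | 11.63 - 11.39 = +0.24 |
| SD of change | 0.45/2.78 × 4.472 = 0.724 | 0.24/1.40 × 4.472 = 0.767 |

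**3. Between-arm differences, dienogest minus NAC.**

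Difference in change, 38 df:
- VAS: -5.75 + 3.60 = -2.15; SE = sqrt((3.32² + 2.48²)/20) = 0.927; 95% CI -4.03 to -0.27; P = 0.026.
- Hemoglobin: 0.45 - 0.24 = 0.21; SE = sqrt((0.724² + 0.767²)/20) = 0.236; 95% CI -0.27 to 0.69; P = 0.38.

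Baseline-adjusted (ANCOVA), 37 df. The before-after correlation is r = (s₁² + s₂² - s_change²)/(2 s₁ s₂). For VAS it is 0.21 (dienogest) and -0.02 (NAC); for hemoglobin, 0.90 and 0.87. Adjusted difference = post-treatment difference - pooled slope × baseline difference.
- VAS: slope 0.116; -2.35 - 0.116 × (-0.20) = -2.33; SE 0.651; 95% CI -3.64 to -1.01; P = 0.001.
- Hemoglobin: slope 0.825; -0.64 - 0.825 × (-0.85) = 0.06; SE 0.231; 95% CI -0.41 to 0.53; P = 0.79.

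Rounding in the published summaries does not alter this reading. Varying each input by ±0.005 keeps the VAS change P within 0.025 to 0.027 and the hemoglobin P at 0.33 or more (change) and 0.71 or more (adjusted).

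**4. Volume and PBAC.** Median volume rose from 15.53 to 19.54 cm³ on dienogest (+4.01, 26%) and from 9.00 to 13.13 cm³ on NAC (+4.13, 46%). These are differences between medians, not median changes. Table 7 compares levels before and after separately (post-treatment P = 0.63), without adjustment for those baselines. No adjusted volume or PBAC difference can be rebuilt from medians and quartiles.

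For PBAC, the post-treatment Z = 4.10 gives P = 0.00004, consistent with the printed 0.00. Two other entries do not agree. The baseline row of Table 9 pairs Z = 0.9 with P = 0.86, but Z = 0.9 gives P = 0.37. The post-treatment upper quartile on dienogest is 9.00 in Table 9 and 8.50 in Table 11.

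**The case against.** The strongest reply is that beating a randomised comparator is itself evidence of an effect. If NAC does not worsen pain or bleeding, then lower VAS and PBAC scores on dienogest imply that dienogest does something, and nothing in Table 12 suggests worsening on NAC. This has force for those two outcomes. It needs an assumption that the trial cannot test, because the improvement on NAC is again a before-after change. It is also not the argument the SAP makes, and it does not reach hemoglobin.

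The SAP is also more open than the quoted sentence alone suggests. The verb is hedged, Table 11 is plainly labelled as a before-after comparison, and the between-arm readings are printed in Tables 7 to 10. All of that stands, and it is why the repair is small.

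Some stronger readings go beyond the documents:
- A reader might infer that the volume increase was obscured. It is stated under Tables 7, 11 and 12, and reporting it is not an error.
- A reader might infer that the SAP credits the drug with the whole 5.75-point VAS fall. The comment gives no effect size and makes no such attribution.
- A reader might infer that both drugs enlarge fibroids. That rests on the same within-arm reasoning and fails for the same reason.

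**Conclusion.** The statement is wrong as written. The inference that dienogest is effective rests on within-arm tests in a trial with two active arms and no untreated arm, and one of its three supports, hemoglobin, shows no significant between-arm difference.

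The randomised data support a lower post-treatment VAS on dienogest than on NAC, by about 2.3 points after baseline adjustment (95% CI 1.0 to 3.6), and lower post-treatment PBAC scores, subject to reconciling the PBAC entries. No significant difference was found in volume or hemoglobin level. A reader might infer that dienogest is therefore ineffective, or that the drugs are equivalent on hemoglobin. Neither follows: the adjusted hemoglobin interval (-0.41 to 0.53) means only that a difference was not demonstrated.

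The adjusted and change-score figures are approximate. They are rebuilt from rounded summaries and assume 20 women per arm in every comparison. The post-treatment VAS on dienogest is skewed (mean 1.35, SD 2.35, range 0 to 8), so the patient-level analysis should confirm the VAS estimate. The main conclusion depends on the design and on Table 10, not on these reconstructions.

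**What to change.** 1. Replace the inference under Table 11 with a between-arm statement that leads with the primary outcome, for example: *At 3 months the groups did not differ significantly in leiomyoma volume (Table 7), and volume had risen within both arms (Tables 11, 12). Post-treatment VAS and PBAC scores were lower with dienogest than with NAC (Tables 8, 9). Hemoglobin levels did not differ significantly between groups (Table 10).*
2. From the existing patient-level data, report baseline-adjusted between-arm differences with 95% CIs for all four outcomes: volume on the log or percentage-change scale (the protocol's sample size justification is framed on percentage change), VAS, PBAC by a rank-based or other method suited to skew, and hemoglobin.
3. Cite that new analysis for any statement about hemoglobin change. Table 10 compares levels before and after separately and contains no test of change.
4. Before PBAC carries a conclusion, reconcile the baseline Z and P in Table 9, and the dienogest upper quartile between Tables 9 and 11.
5. Keep Tables 11 and 12 as descriptive within-arm summaries.

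The cost is one sentence rewritten, a check of two table entries, and a small re-analysis with no new data. The standalone efficacy statement is lost. The comparative results on pain and, once reconciled, bleeding remain.

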### **Sample size Justification:**

Assuming an effect size of 1.0 reflecting the percentage change (reduction) in the volume of uterine leiomyoma, a sample of 12 patients in each group will be enough to detect such rate, if true, at 0.01  $\alpha$  error and 0.90 power of the test. We will increase the sample to 20 cases in each group to maximize the power of the study.

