**Table 6: Comparison between two groups regarding clinical examination of patients:**

	Group A (Dienogest) (N=20)			Group B (NAC) (N=20)			t*	P value
	Range	Mean	SD	Range	Mean	SD		
Temperature	37.00-37.00	37.00	0.00	37.00-37.00	37.00	.00	-	-
Pulse	65.00-85.00	76.90	6.04	73.00-88.00	80.65	3.95	2.32	0.03
Systolic BP	90.00-120.00	110.50	9.45	90.00-120.00	106.00	8.83	1.56	0.13

Diastolic BP		60.00-80.00	72.00	8.34	60.00-80.00	67.00	8.65	1.86	0.07		
		N	%		N	%		$\chi^2$ **	P value		
General appearance	Normal	20	100.0%		20	100.0%		-	-		
Pallor	No	19	95.0%		20	100.0%		1.03 FE	1.00		
	Yes	1	5.0%		0	0.0%					
Abdominal obstetric examination	Free	20	100.0%		19	95.0%		1.03 FE	1.00		
	Distended abdomen	0	0.0%		1	5.0%					
local examination	Free	16	80.0%		11	55.0%		3.69 FE	0.22		
	Vaginal bleeding	2	10.0%		7	35.0%					
	Bulky uterus	2	10.0%		2	10.0%					

\*Student t test

\*\*Chi square test (FE: Fisher Exact)

The only significant difference observed is in the pulse rate, with Group B having a slightly higher mean pulse rate ( $p = 0.03$ ). Other clinical parameters like temperature, systolic, and diastolic blood pressure do not differ significantly between the groups ( $P$  value  $>0.05$ ).

[figure not shown]

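### The protocol's only alpha is 0.01, but the SAP mostly reads P-values against an undeclared 0.05; the within-group hemoglobin gain on dienogest is the one outcome result whose status depends on which applies.

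*SAP*

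**What the plan says.** **Protocol, Sample size Justification.** The effect size is set at 1.0 for percentage change in leiomyoma volume. The paragraph then states: "a sample of 12 patients in each group will be enough to detect such rate, if true, at 0.01". That last figure is the alpha; power is given as 0.90. The sample is then raised to 20 per group. This is the only alpha in the protocol. It is attached to the primary volume outcome. Nothing says whether it is one- or two-sided, or whether it also applies to secondary outcomes or within-group tests.

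**SAP, comments under the tables.** No sentence in the available text sets a significance level. The comments under Tables 1, 5, 6, 7 and 10 treat P above 0.05 as not significant; for between-group hemoglobin (Table 10) the wording is "the differences between the groups are not statistically significant". For pulse in Table 6, with P = 0.03, it is "The only significant difference observed is in the pulse rate, with Group B having a slightly higher mean pulse rate". In Table 4 the detailed count of abortions also has P = 0.03, yet the comment reports no significant difference for abortion history. The collapsed yes/no row for that variable has P = 0.11, and the text does not say which row the comment refers to.

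**SAP, Table 11 (dienogest, before versus after).** Hemoglobin rises from 10.54 to 10.99 (t = 2.78, printed P 0.01). Median leiomyoma volume rises from 15.53 to 19.54 cm³ (Z = 2.78, printed P 0.01). The comment reads: "Significant improvements are observed in VAS scores, HMB assessment, and hemoglobin levels after treatment". From these three results it infers that the drug works. It also reports the volume increase as significant.

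**The concern.** A trial should have one stated rule for calling a result significant. Here the protocol gives one number and the SAP's comments imply another, five times larger, with no explanation of the change. Even the implied 0.05 is not applied evenly: P = 0.03 is called significant in Table 6 and passed over in Table 4.

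Printing P to two decimals hides the consequence. In Table 11 two results appear as 0.01, and a reader holding the protocol's alpha cannot tell that they fall on opposite sides of it. At stake is one of the three results offered in favour of dienogest. The choice of alpha also changes the power behind the null between-arm volume result.

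**Working it through.** **1. Are the SAP's P-values two-sided?** Pulse, t = 2.32 on 38 df, gives two-sided P = 0.026 (printed 0.03). NAC hemoglobin, t = 1.40 on 19 df, gives 0.178 (printed 0.18). Yes, so a two-sided reading is used below.

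**2. Dienogest hemoglobin, Table 11 (n = 20, df = 19).**
- P = 2 × Pr(T₁₉ > 2.78) = 0.0119, and 0.0118 to 0.0121 over the rounding of t (2.775 to 2.785). This reproduces the printed 0.01.
- The two-sided critical value at 0.01 is 2.861, and 2.78 falls short of it. At 0.05 it is 2.093, and 2.78 exceeds it.
- Mean change 10.99 − 10.54 = 0.45; standard error 0.45 / 2.78 = 0.162.
- 95% CI: 0.45 ± 2.093 × 0.162 = 0.11 to 0.79. 99% CI: 0.45 ± 2.861 × 0.162 = −0.01 to 0.91.
- Read one-sided, P = 0.006 (critical value 2.539), which would pass 0.01.

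**3. Other dienogest results in Table 11.** Volume, Z = 2.78: P = 0.0054. PBAC, Z = 2.88: P = 0.0040 (printed 0.004, so three decimals were available). VAS, t = 7.74 on 19 df: P below 0.001. All three meet 0.01.

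**4. Does any other outcome result fall between 0.01 and 0.05?**

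| Comparison | P | At 0.05 | At 0.01 |
|---|---|---|---|
| Between arms, volume after (Table 7) | 0.63 | no | no |
| Between arms, VAS after (Table 8) | 0.0008 recomputed | yes | yes |
| Between arms, PBAC after (Table 9, Z = 4.10) | <0.001 recomputed | yes | yes |
| Between arms, hemoglobin after (Table 10) | 0.17 | no | no |
| NAC, VAS (Table 12, t = 6.49) | <0.001 recomputed | yes | yes |
| NAC, hemoglobin (Table 12) | 0.18 | no | no |
| NAC, volume (Table 12, Z = 3.46) | 0.0005 recomputed | yes | yes |
| NAC, PBAC (Table 12) | 0.08 | no | no |

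Only dienogest hemoglobin changes status.

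**5. Randomized comparison of hemoglobin change.** The standard errors of change follow from the paired t values: 0.45 / 2.78 = 0.162 for dienogest and (11.63 − 11.39) / 1.40 = 0.24 / 1.40 = 0.171 for NAC. Then t = (0.45 − 0.24) / √(0.162² + 0.171²) = 0.21 / 0.236 = 0.89, P about 0.38 on 38 df.

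**6. The protocol's sample size figures.** For a two-sided two-sample t test with standardized difference d = 1.0 and n per group, df = 2n − 2 and the noncentrality is d√(n/2).

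| n per group | Noncentrality | Power at 0.01 | Power at 0.05 |
|---|---|---|---|
| 12 | 2.449 | 38% | 65% |
| 20 | 3.162 | 67% | 87% |

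Reaching 90% needs 32 per group at 0.01 or 23 at 0.05. A one-sided test at 0.01 still needs 28. The stated 12 per group is not reproduced at either level.

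**The case against.** The strongest reply is that hemoglobin has no planned threshold to fail. The protocol's 0.01 is a sizing input for percentage change in volume, while hemoglobin is a component of a secondary outcome, tested here within one arm. Sizing a trial at a stricter alpha than the one later used for testing is not in itself a contradiction. That stands. A reader might infer that the SAP broke a trial-wide 0.01 rule and that the hemoglobin claim is therefore wrong; the protocol states no such rule. It can only be said that the result misses the protocol's one alpha when that alpha is read two-sided.

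Three further points stand:
- The SAP applies 0.05 without declaring it, and does not apply it throughout, as the abortion row shows. Its opening pages were not available, so a declaration there cannot be excluded.
- The figure 0.012 is recomputed; the table prints 0.01.
- Pulse is a baseline characteristic, so relabelling it decides nothing about treatment.

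A reader might also infer that the looser level inflates false positives among the trial's between-arm outcome tests. That does not bear on this point: none of those four conclusions differs between 0.05 and 0.01, and the affected result lies outside that set.

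Finally, it can be argued that the 0.01 is itself a slip, since the sizing figures around it do not reproduce. They do not reproduce at 0.05 either, so this does not settle which level was meant. It adds to the reasons for correcting the paragraph.

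**Conclusion.** The concern holds in a limited form. The two documents do not share a stated significance level, and the level implied by the SAP is applied unevenly. One outcome statement depends on it: the within-group hemoglobin gain on dienogest, 0.45 (g/dL, the usual unit, assumed because the table prints none), P = 0.012, significant at two-sided 0.05 but not at two-sided 0.01. The significant volume increase in the same arm meets both levels. No between-arm outcome conclusion changes.

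This rests on a two-sided reading, which matches the SAP's printed P-values but is not stated in the protocol, and on the reported t, Z and n. The power figures assume that the protocol's effect size of 1.0 is a standardized mean difference between arms.

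Whichever level is chosen, the hemoglobin result is weak evidence for dienogest. It is an uncontrolled before-and-after test, and the randomized comparison shows no difference at either level (P = 0.17 after treatment; about 0.38 for change).

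**What to change.** In both documents, state one alpha, whether it is one- or two-sided, and which tests it governs (primary, secondary, within-group, baseline). Print P-values to three decimals, with <0.001 in place of 0.00.

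- **If two-sided 0.01 governs all tests:** remove hemoglobin from the list of significant improvements under Table 11, and stop calling the pulse difference significant in Table 6.
- **If 0.05 is meant:** correct the alpha in the protocol's sample size paragraph, and reconcile the comment on abortions under Table 4 with its P = 0.03 row.
- **In either case:** replace the claim of 90% power with 12 per group. At effect size 1.0 and a two-sided two-sample t test, give the power for the planned 20 per group: about 67% at 0.01 or 87% at 0.05. Beside the Table 11 statement, note that the randomized hemoglobin comparison in Table 10 (P = 0.17) is not significant.

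The cost is wording in both documents and reprinted P-values. No new data are needed. Under the 0.01 option, one favourable statement about dienogest is lost.
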